## 2 PROTOCOL OBJECTIVES

### 2.1 Primary

PO1: To determine baseline and post-vaccination influenza antibody titers by hemagglutination inhibition (HAI) against cclIV4 vaccine antigens following concomitant administration with mRNA vaccine or alone.

### 2.2 Exploratory

EO1: To determine baseline and post-vaccination influenza antibody titers by microneutralization (MN), in a subset of samples, against cclIV4 vaccine antigens following concomitant administration with mRNA vaccine or alone.

EO2: To determine baseline and post-vaccination SARS-CoV-2 antibody binding titers and ACE2 binding inhibition and viral neutralization, on a subset of specimens, against Moderna mRNA COVID-19 vaccine antigens following concomitant administration with cclIV4 or alone.

EO3: To determine duration and rate of waning of influenza HAI and MN antibody titers against cclIV4 vaccine antigens and circulating influenza viruses.

EO4: To determine duration of and rate of waning of SARS-CoV-2 antibody titers and viral neutralization titers, on a subset of samples, against Moderna mRNA COVID-19 vaccine antigens and circulating SARS-CoV-2 variants.

EO5: To determine influenza HAI and MN antibody titers against circulating influenza viruses during baseline and post-vaccination or post-infection.

EO6: To determine SARS-CoV-2 antibody binding titers and viral neutralization titers (in a subset of samples) against circulating SARS-CoV-2 variants during baseline and post-vaccination.

EO7: To compare the frequencies of antigen-specific T and B cells utilizing conventional ELISPOT assays, high-dimensional flow cytometric analysis of innate and adaptive immune cell

phenotype characterization using fluorochrome-conjugated antigen tags, and intracellular cytokine staining to 2023-24 cclIV4 and mRNA COVID-19 vaccines administered either concomitantly or sequentially, 28 days apart.

EO8: To compare transcriptome, B cell receptor (BCR) and T cell receptor (TCR) diversity of antigen-specific cells and assess serological antibody repertoire (clonotypes) using 10X genomics platform, and liquid chromatography/mass spectroscopy in a subset of participants.

EO9: To investigate the waning of antigen-specific B cells and antibody clonotypes in a subset of participants.

EO10: To describe safety of concomitant versus sequential administration of cclIV4 and mRNA COVID-19 vaccination.

### 3 STUDY ENDPOINTS

#### 3.1 Primary

- i. Proportion of participants in each vaccination group with a seroprotective HAI (in a subset of samples) titer ( $\geq 1:40$ ) pre- and post-cclIV4 immunization for each 2023-24 influenza vaccine antigen
- ii. Proportion of participants in each vaccination group achieving HAI seroconversion (a titer  $\geq 1:40$  following cclIV4 if the baseline titer is  $< 1:10$  or a four-fold rise in titer if the baseline titer is  $> 1:10$ ) following cclIV4 vaccination for each 2023-24 influenza vaccine antigen
- iii. HAI GMT for each 2023-24 influenza vaccine antigen pre- and post-cclIV4 in each vaccination group
- iv. GMFR in HAI titers for each 2023-24 influenza vaccine antigen in each vaccination group

#### 3.2 Exploratory

EO1:

- I. Proportion of participants in each vaccination group with a seroprotective MN (in a subset of samples) titer ( $\geq 1:40$ ) pre- and post-cclIV4 immunization for each 2023-24 influenza vaccine antigen
- II. Proportion of participants in each vaccination group achieving MN (in a subset of samples) seroconversion (a titer  $\geq 1:40$  following cclIV4 if the baseline titer is  $< 1:10$  or a four-fold rise in titer if the baseline titer is  $> 1:10$ ) following cclIV4 vaccination for each 2023-24 influenza vaccine antigen
- III. HAI (in a subset of samples) MN for each 2023-24 influenza vaccine antigen pre- and post-cclIV4 in each vaccination group
- IV. GMFR in MN (in a subset of samples) titers for each 2023-24 influenza vaccine antigen in each vaccination group

EO2. GMT for SARS-CoV-2 binding antibody titer and viral neutralization titer (for a subset of samples) pre- and post-vaccination with mRNA COVID-19 vaccine

EO3:

- I. HAI and MN GMT for each 2023-24 influenza vaccine and circulating influenza virus antigens at visit 1, visit 2, visit 3, and visit 4 for each vaccination group
- II. Geometric mean fold change in HAI and MN titers for each vaccination group from visit 1 to visit 2, visit 3, and visit 4 for each 2023-24 influenza vaccine and circulating influenza virus antigen

EO4:

- I. SARS-CoV-2 binding antibody and viral neutralization GMT for each mRNA COVID-19 vaccine and circulating SARS-CoV-2 virus antigens at visit 1, visit 2, visit 3, and visit 4 for each vaccination group
- II. Geometric mean fold change in SARS-CoV-2 and viral neutralization (in a subset of samples) titers for each vaccination group from visit 1 to visit 2, visit 3, and visit 4 for each COVID-19 Moderna mRNA COVID-19 vaccine and circulating SARS-CoV-2 virus antigen

EO5

- I. Proportion of participants in each vaccination group with a seroprotective titer ( $\geq 1:40$ ) pre- and post-cclIV4 immunization (visits 1-3) and/or pre- and post-influenza infection (acute and convalescent visits), if applicable, for each 2023-24 circulating influenza virus antigen
- II. Proportion of participants in each vaccination group achieving seroconversion (a titer  $\geq 1:40$  following cclIV4 if the baseline titer is  $< 1:10$  or a four-fold rise in titer if the baseline titer is  $> 1:10$ ) following cclIV4 vaccination (visit 1 to visits 2-3) and/or influenza infection (acute to convalescent visits), if applicable, for each 2023-24 circulating influenza virus antigen
- III. HAI and MN GMT for each 2023-24 circulating influenza virus antigen pre- and post-cclIV4 (visits 1-3) and/or pre- and post-influenza infection (acute and convalescent visits), if applicable, in each vaccination group
- IV. GMFR in HAI or MN titers for each vaccination group following cclIV4 vaccination (visit 1 to visits 2-3) and/or influenza infection (acute to convalescent visits), if applicable, for each 2023-24 circulating influenza virus antigen

EO6:

- I. SARS-CoV-2 binding antibody and viral neutralization (for a subset of samples) titers GMT at pre- and post-vaccination (visits 1-3) and/or pre- and post-SARS-CoV-2 infection (acute and convalescent visits), if applicable, against 2023-24 circulating SARS-CoV-2 virus antigens
- II. GMFR in SARS-CoV-2 binding antibody and viral neutralization (for a subset of samples) titers following mRNA COVID-19 vaccination (visit 1 to visits 2-3) and/or SARS-CoV-2 infection (acute to convalescent visits), if applicable, against 2023-24 circulating SARS-CoV-2 virus antigens

EO7:

- I. The frequency of antigen-specific T and B cells to influenza and SARS-CoV-2 at visit 1, visit 2, visit 3, visit 4, and acute and convalescent visits, if applicable
- II. High-dimensional flowcytometric analyses of innate and adaptive immune cells
- III. ELISPOT evaluation for SARS-CoV-2 memory B cells

EO8: BCR and TCR diversity and clonal dominance (antibody clonotypes) of serological repertoire in a subset of participants

EO9: The frequency of antigen-specific B cells and clonal dominance (antibody clonotypes) to influenza and SARS-CoV-2 at visit 1, visit 2, visit 3, visit 4, and acute and convalescent visits (if applicable) in a subset of participants

E10:

- I. Number and percent of participants reporting fever or injection site and/or systemic reactions during the first 3 days following each vaccination visit stratified by severity and, for those reporting symptoms, their impact on health
- II. Number and percent of participants reporting a change in health status requiring hospital admission (including a description of the event) during the study period

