
Determine duration of and rate of waning of SARS-CoV-2 antibody titers and viral neutralization titers, on a subset of samples, against mRNA COVID-19 vaccine antigens and circulating SARS-CoV-2 variants
	
i. SARS-CoV-2 binding antibody and viral neutralization GMT for each mRNA COVID-19 vaccine and circulating SARS-CoV-2 virus antigens at visit 1, visit 2, visit 3, and visit 4 for each vaccination group
 
ii. Geometric mean fold change in SARS-CoV-2 and viral neutralization (in a subset of samples) titers for each vaccination group from visit 1 to visit 2, visit 3, and visit 4 for each COVID-19 Moderna mRNA COVID-19 vaccine and circulating SARS-CoV-2 virus antigen

Determine influenza HAI and MN antibody titers against circulating influenza viruses during baseline and post-vaccination or post-infection
	
i. Proportion of participants in each vaccination group with a seroprotective titer ($\geq 1:40$) pre- and post-cclIV4 immunization (visits 1-3) and/or pre- and post-influenza infection (acute and convalescent visits), if applicable, for each 2023-24 circulating influenza virus antigen
 
ii. Proportion of participants in each vaccination group achieving seroconversion (a titer $\geq 1:40$ following cclIV4 if the baseline titer is $< 1:10$ or a four-fold rise in titer if the baseline titer is $> 1:10$) following cclIV4 vaccination (visit 1 to visits 2-3) and/or influenza

	
infection (acute to convalescent visits), if applicable, for each 2023-24 circulating influenza virus antigen
 
iii. HAI and MN GMT for each 2023-24 circulating influenza virus antigen pre- and post-ccllV4 (visits 1-3) and/or pre- and post-influenza infection (acute and convalescent visits), if applicable, in each vaccination group
 
iv. GMFR in HAI or MN titers for each vaccination group following ccllV4 vaccination (visit 1 to visits 2-3) and/or influenza infection (acute to convalescent visits), if applicable, for each 2023-24 circulating influenza virus antigen

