Demographic and health data (including influenza and COVID-19 vaccination and infection history) will be collected upon enrollment and verified after enrollment via electronic medical record extraction. Enrolled participants will be randomized to one of the following interventions (2:1:1) using a permuted block method stratified by age group (aged 6-11 years and 18-64 years) and site: (i) concomitant administration of the mRNA COVID-19 vaccine (Moderna) and quadrivalent influenza vaccine (cclIV4); (ii) sequential administration of the quadrivalent influenza vaccine (cclIV4) at Visit 1 (day 0) and the mRNA COVID-19 vaccine (Moderna) at Visit 2 (day 28); (iii) sequential administration of the mRNA COVID-19 vaccine (Moderna) at Visit 1 (day 0) followed by the quadrivalent influenza vaccine (cclIV4) at Visit 2 (day 28). Whole blood samples to isolate sera, PBMC and plasma (target to collect PBMC and plasma samples at every visit from a subset of 250 participants; 200 adults and 50 children) will be collected prior to vaccination administration at Visit 1 (day 0) and Visit 2 (day 28). Participants will not be blinded to vaccine group and will receive two vaccines in separate limbs (for the concomitant vaccination [group i]) or one vaccine at Visit 1 (day 0) and a second vaccine at Visit 2 (day 28) (for sequential vaccination [groups ii and iii]) in an unblinded manner.

Participants will provide a blood sample for isolation of serum, PBMC, and plasma (target to collect PBMC and plasma samples at every visit from a subset of 250 participants; 200 adults and 50 children) at Visit 3 (day 56; post-vaccination 2) and Visit 4 (day 180; end of local flu circulation). If participants exhibit ARI during the study period, they may be asked to present for

an acute (<10 days after symptom onset) and convalescent (28 days after acute visit) visit to provide a nasal swab for viral testing (acute visit only) and blood sample for isolation of serum, PBMC, and plasma (acute and convalescent visit for those with positive viral molecular test for influenza or SARS-CoV-2). Influenza virus and SARS-CoV-2 serologic and cellular immunity testing will be conducted at CDC and/or a CDC-approved site.

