## 4 STUDY DESIGN

### 4.1 Study Description

This study is a randomized immunogenicity study in an enrolled cohort with active surveillance for acute respiratory illness (ARI). During this study, participants will be randomly assigned to receive an approved quadrivalent influenza vaccine (Flucelvax [cclIV4]) and mRNA COVID-19 vaccine (Moderna) either concomitantly (given in contralateral arms) or sequentially (28 days apart).

Blood samples from participants will be collected for measurement of biomarkers of immune response at baseline (visit 1; day 0), post-vaccination 1 (visit 2; day 28), post-vaccination 2 (visit 3; day 56), and post-season (visit 4; day 180). Serum and peripheral blood mononuclear cells (PBMC) and plasma (target to collect PBMC and plasma samples at every visit from a subset of approximately 250 participants; 200 adults and 50 children) samples will be isolated from whole blood and tested for biomarkers of vaccine immunogenicity, and duration of antibody responses.

Participants will receive electronic surveys via email or text message three days after each vaccination asking about vaccine reactogenicity and weekly asking about change in health status and new ARI symptoms; those reporting illness may be asked to provide a respiratory swab for laboratory testing for influenza and SARS-CoV-2 and up to 2 additional blood draws (acute [< 10 days after symptom onset] and convalescent [28 days after acute visit if lab-confirmed positive for influenza or SARS-CoV-2]).

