## 6.3 Influenza Immunogenicity Population

The Influenza Immunogenicity Population is a subset of the mITT Population that includes only subjects who received both vaccines, provide visit 1 and visit 2 blood draws available with HAI titer results for analysis within the protocol-defined time frame, did not have an influenza or SARS-CoV-2 infection between visits 1 and 2, and had no protocol violations affecting immunogenicity. Protocol violations affecting the immunogenicity analyses are defined in the Statistical Analysis Plan (SAP) Appendix 1. The acceptable visit window for sample analysis will be +14 days from the target date. Should 10% or more of the total study population be excluded from the Influenza Immunogenicity Population due to missing the visit window, then an additional analysis will be performed including these subjects with the missing visit window exclusion.

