## 9.2 Exploratory Objectives

Serology and cell mediated immunity objectives will be analyzed using the immunogenicity population. All exploratory endpoints will be assessed with two-sided tests and alpha set to 0.05.

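### The infection parts of EO5 and EO6 label a post-onset sample pre-infection, drop early infections, and can count vaccine response as infection response

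*SAP*

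**What the plan says.** **Endpoints.** SAP 3.2 gives the infection titres in EO5 as "pre- and post-influenza infection (acute and convalescent visits") and in EO6 as "pre- and post-SARS-CoV-2 infection (acute and convalescent visits"). Seroconversion and fold rise in EO5 are taken "following cclIV4 vaccination (visit 1 to visits 2-3) and/or influenza infection (acute to convalescent visits), if applicable". Protocol 4.2 matches, with "infection (acute to convalescent visits), if applicable, for each 2023-24 circulating influenza virus antigen".

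**Timing.** Protocol 5.1 describes "an acute (<10 days after symptom onset) and convalescent (28 days after acute visit) visit". SAP 4.1 agrees: "acute [< 10 days after symptom onset] and convalescent [28 days after acute visit if lab-confirmed positive for influenza or SARS-CoV-2"). The acute visit is prompted by a weekly symptom survey (Protocol 5.5.2.2). Acute and convalescent bleeds may coincide with scheduled visits (Protocol 5.4.1).

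**Population.** SAP 9.2 states: "Serology and cell mediated immunity objectives will be analyzed using the immunogenicity population". SAP 6.3 and 6.4 both restrict that population to participants who "did not have an influenza or SARS-CoV-2 infection between visits 1 and 2".

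**Method.** SAP 9.2 gives the SARS-CoV-2 and circulating-virus objectives the same methods as the primary HAI objective, and SAP 9.1 defines those as group i against group ii. SAP 10 defines fold rise and seroconversion relative to vaccination only.

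**The concern.** Three features of a vaccine-response analysis have been carried over to infection endpoints.

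- The baseline is called pre-infection although it is drawn during illness. Sera from days 0, 28 and 56 are planned for everyone, but the infection endpoints do not use them.
- The exclusion of early infections suits a vaccine-response population. Applied to an infection endpoint, it removes part of what is to be described. It drops participants, not episodes: someone with influenza between Visits 1 and 2 also loses a SARS-CoV-2 infection months later.
- Vaccine and infection responses are joined by an and/or, and no text deals with time since vaccination in infected participants. A titre rise caused by a vaccine given at Visit 2 can be reported as a response to infection.

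At stake is whether a fold rise reported under EO5 or EO6 can be attributed to infection and, in EO6, whether a difference between groups reflects the vaccination schedule or only the age of the last dose.

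**Working it through.** The plan gives no sample size, expected number of infections, titre SD or antibody kinetics for these endpoints, so it has no figure to reproduce.

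**1. Timing (from the documents).** The acute bleed is 0-9 days after onset and the convalescent bleed 28-42 days later (Protocol 5.4.1, Table 2). The convalescent bleed is therefore 0 + 28 = 28 to 9 + 42 = 51 days after onset. No acute bleed precedes onset.

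**2. Follow-up removed by the exclusion (from the documents).** Visit 2 is on day 28 (window 28-42), and Visit 4 is 152 ± 30 days after Visit 2 (Protocol Table 1).
- Target days: 28/180 = 15.6%.
- Lowest: 28/(28 + 152 + 30) = 28/210 = 13.3%.
- Highest: 42/(42 + 152 - 30) = 42/164 = 25.6%.

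These are shares of time. They are shares of infections only if infections are evenly spread.

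**3. Where vaccine response enters the interval (from the documents).**

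| Group | Influenza vaccine | COVID-19 vaccine |
|---|---|---|
| i | Visit 1 | Visit 1 |
| ii | Visit 1 | Visit 2 |
| iii | Visit 2 | Visit 1 |

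Take a SARS-CoV-2 infection with the acute bleed 5 days after Visit 2. In group ii that bleed is 5 days after the COVID-19 dose and the convalescent bleed is 5 + 28 = 33 to 5 + 42 = 47 days after it. In group i the acute bleed is already 28 + 5 = 33 to 42 + 5 = 47 days after the dose. For influenza, groups i and ii are both dosed at Visit 1; only group iii is in the exposed position.

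**4. Size of the mixing (assumed values).** Let F be the true geometric mean fold rise, p the share of the log rise already present at the acute bleed, and V the vaccine-driven fold rise inside the interval. Then observed = F^(1-p) × V. With F = 8 and p = 0.25:
- No vaccine response in the interval (V = 1): 8^0.75 = 4.76.
- V = 1.5, 2 or 4: 7.14, 9.51 or 19.03.

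For infections in that position, the ratio of group ii to group i is V if F and p are alike in both groups. Across all analysed infections it is smaller. If infections are evenly spread over the 152 days after Visit 2, acute bleeds within 28 days of Visit 2 make up 28/152 = 18.4%. The ratio is then V^0.184: 1.08, 1.14 or 1.29 for V = 1.5, 2 or 4. This gives every such bleed the full V, so it leans high.

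**5. Attenuation from the acute baseline (assumed kinetics).** Spread acute bleeds evenly over days 2-9 after onset. Let the rise start on day 3-7 and finish on day 12-16, linear on the log scale.
- Largest p (start 3, end 12): (6²/18)/7 = 0.29.
- Smallest p (start 7, end 16): (2²/18)/7 = 0.03.
- A true 8-fold rise reads 8^0.71 = 4.4 to 8^0.97 = 7.5.
- A true 4-fold rise reads 2.7 to 3.8.

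The four-fold-rise rate is 1 - Φ((2 - log2 GMFR)/SD). With an assumed log2 SD of 1.5 and true GMFR 8, it falls from 74.8% (p = 0) to 56.6% (p = 0.25). At p = 0 there is no loss.

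**6. Net direction.** At F = 8 and p = 0.25, V = 1.5 gives 7.14, below the truth, and V = 2 gives 9.51, above it. The sign depends on values that the documents do not give.

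**The case against.** The strongest reply is that the damage is narrow. Much of it stands.

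- **EO5 comparison.** Groups i and ii both receive influenza vaccine on day 0 and infections before Visit 2 are excluded, so every influenza infection compared follows vaccination by about 28 days or more. A reader might infer that this comparison is not interpretable; the documents do not support that.
- **EO6 comparison.** If group i were compared with group iii, both would have had COVID-19 vaccine on day 0. True, but the SAP does not name that pairing. Read literally, its method is group i against group ii.
- **The exclusion.** A reader might infer that it causes the infection response to be understated. It does not lower any measured rise, and it removes the infections closest to the Visit 1 dose. It limits who is described.
- **Late acute sampling.** All groups follow the same weekly survey. With similar timing, sampling shrinks the log ratio and does not create a difference. The convalescent GMT is not lowered at all.
- **Baseline choice.** Visits 3 and 4 are 180 - 56 = 124 days apart, so the last scheduled serum may be months old. Replacing the acute baseline outright would be a trade, not a correction.
- **Early infections.** Most of those re-admitted have the relevant vaccine inside, or less than 28 days before, their sampling interval. The gain is complete reporting, with few extra rises attributable to infection alone.
- **Scope.** EO6 as worded concerns baseline and post-vaccination titres, infection enters only where applicable, and acute visits are optional.

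What the reply leaves standing is the label, the mismatch between population and endpoint, and the missing rule on vaccine timing.

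**Conclusion.** The point holds for the infection parts of EO5 and EO6. As written, the plan labels an illness sample pre-infection, drops participants infected during about 16% of follow-up on target days (13-26% across visit windows), and lets a Visit 2 vaccine response count as infection response. Under the literal group i against group ii method, this can inflate the group ii infection rise in EO6: by the factor V in infections soon after Visit 2, and by roughly 1.08 to 1.29 overall if infections are evenly spread and V is 1.5 to 4. In EO5 it affects only group iii's per-group summary.

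A reader might go further and conclude that infection responses are understated overall. That is not established: attenuation rests on assumed kinetics and can be close to nil, while vaccine mixing pulls upward. Nor does the mean attenuation show that a given participant with a true four-fold rise would fail the threshold.

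These endpoints are exploratory, the number of infections may be small, and the primary HAI endpoints use neither acute nor convalescent sera. This is a cheap improvement and does not threaten the main result.

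**What to change.** Three changes to SAP 3.2, 6, 9.2 and 10:

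1. Define a separate infection-response set: all mITT participants with a positive test and paired acute and convalescent sera, whenever infected. State which mITT definition applies, since Protocol 8.1 requires at least one vaccine and SAP 6.2 requires both.
2. Report infection and vaccination responses separately, with their own fold-rise and seroconversion definitions. Present infection responses by time since the study vaccine against that virus. Do not attribute to infection alone any rise whose sampling interval contains that vaccine or starts less than 28 days after it. Name the groups compared in EO6.
3. Call the acute sample acute. Keep acute-to-convalescent as the main interval and add the last scheduled serum before onset as a sensitivity baseline.

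The cost is SAP wording, with matching text in Protocol 4.2; the sera are already planned. The downsides are smaller strata in what may be few infections, and waning or vaccine response in the older baseline serum, which is why it belongs in a sensitivity analysis.
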